## 11 STATISTICAL CONSIDERATIONS

The material of [Section 11](#) of the clinical trial protocol is the basis for the Statistical Analysis Plan (SAP) for the study. This plan may be revised during the study to accommodate clinical trial protocol amendments and to make changes to adapt to unexpected issues in study execution and data that affect planned analyses. These revisions will be based on blinded review of the study and data, and a final plan will be issued at the latest 6 to 8 weeks before final database lock.

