2.4.4 Analyses of efficacy endpoints

2.4.4.1 Analysis of primary efficacy endpoint(s)

The statistical test for the primary efficacy endpoint, the mean change from baseline measure of pain relief (WOMAC A1) between Hylan G-F 20 and placebo over 26 weeks, will be 2-sided at α level of 0.05.

For the primary efficacy endpoint, the following null hypothesis and alternative will be tested:

H0: Hylan G-F 20 is not superior to placebo

H1: Hylan G-F 20 is superior to placebo

The primary effectiveness analysis will be performed on the mITT population and will be based on repeated-measures Analysis of Covariance (ANCOVA) that will be used to test for differences in treatment efficacy, as quantified by the change from baseline in WOMAC A1 over 26 weeks between Hylan G-F 20 and placebo. The repeated measures ANCOVA model is equivalent to mixed model for repeated measures (MMRM) and will include terms for treatment, site, visit and visit-by-treatment interaction, as well as the baseline WOMAC A1 score as a covariate.

The difference between Hylan G-F 20 group and placebo group and its corresponding 95% confidence interval will be estimated within the framework of ANCOVA. An unstructured variance-covariance structure will be used to model the within-patient errors. If this model fails to converge, the following structures will be tested in this order: Toeplitz (equal variances and a separate correlation for each level of separation between the time points), AR (1) (first-order autoregressive, equal variances and exponentially decreasing correlations), CS (compound symmetry, equal variances and equal pairwise correlations across fixed time points). The first (co)variance structure yielding convergence will be used as the primary analysis.

The Kenward-Roger approximation will be used to estimate denominator degrees of freedom. Outcomes between patients are assumed to be independent. The primary comparison will be the contrast between Hylan G-F20 and control over 26 weeks. An example of the SAS code is provided below (note time is modeled with the visit variable):

SAS Display 1 Code for Continuous Endpoints

```
proc mixed data = data method = ml;
class patid randgrp site visit;
model y_chg = site baseline randgrp visit visit*randgrp / ddfm=kr;
repeated visit / type = un subject = patid;
lsmeans randgrp randgrp*visit / cl diff at baseline= baseline;
run;
```

where:

```
randgrp = Hylan G-F20, control
site     = site number

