Each imputed data set will then be analyzed using the same repeated measures analysis of ANCOVA and resulting treatment differences over 26 weeks and their standard errors will then be combined to produce valid statistical inference based on t-tests using the SAS PROC MIANALYZE. Least-squares mean change from baseline over 26 weeks for each treatment group will be calculated and displayed with their associated standard errors. Estimated treatment differences along with corresponding 95% confidence intervals and p-values will also be presented. These analyses will also be performed at each scheduled post-base visit.

The post-withdrawal part of each pattern-specific distribution will be modelled using the following approaches:

- **Missing at Random (MAR) Approach:** The means and variance-covariances following withdrawal are chosen to reflect the subject's own treatment group. This approach will provide similar results to using a mixed effects model where the unstructured covariance matrix is estimated separately for each treatment group.
- **Copy Reference (CR) Approach:** The whole distribution of Hylan G-F20 group even prior to withdrawal is assumed to be the same as the control group. This mimics the case where those withdrawing are in effect non-responders. If a patient on Hylan G-F20 is above the control group mean then this positive residual will feed through into subsequent observations, to a degree determined by the correlation in the control group. The patient's profile will slowly decay back towards the mean for the control group at later visits. For the control group, this is equivalent to the MAR approach above.

It is important to note that the CR approach is conservative and constructed to attenuate the treatment difference estimated from the primary analysis.

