2.4.4.2 Analyses of secondary efficacy endpoints

As with the primary effectiveness analysis, the secondary effectiveness analyses will be performed on the mITT population as well.

For the analysis of the change from baseline in 7-day average WOMAC A1, WOMAC A, PTGA, and COGA, repeated-measures ANCOVA will be used as described in the description of the primary effectiveness analysis.

For the analysis of WOMAC A1 responders (≥ 2 point improvement on NRS Scale) generalized estimating equations (GEE) modeling will be used. Each responder (yes/no) endpoint evaluated at multiple post-baseline visits will be analyzed using GEE for binary outcomes. A GEE model will be fitted to the responder data and will include terms for baseline measure, site, visit, treatment group and a visit-by-treatment group interaction. Hypothesis testing will be performed using least squares means based on the linear predictor of the model.

For the analysis of the percentages of positive responders, patients who discontinued the study prior to the Week 26 assessment due to either target knee-related AEs or due to lack of efficacy were classified as non-responders in the efficacy analysis. Patients who discontinued the study for other reasons had their responder status imputed using the LOCF method. The LOCF was used for all responder analyses, but not for the analysis of other parameters. No replacement on any missing or invalid data was made for the safety analyses.

No sensitivity analyses are planned for secondary efficacy endpoints in this study.

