2.4.4.4 Analyses of tertiary efficacy endpoints and other endpoints

The analyses of tertiary efficacy endpoints and other endpoints will be presented with unadjusted p-values and considered exploratory. As with the primary effectiveness analysis, the tertiary effectiveness analyses and analyses of other endpoints will be performed on the mITT population as well.

For the analyses of the change from baseline in WOMAC A1, 7-day average WOMAC A1, WOMAC A, PTGA and COGA at Week 4, 8, 12, 16, 20, and the change from baseline in WOMAC B, C and total and quality of life at Week 4, 8, 12, 16, 20, 26, the same repeated-measures ANCOVA model as described in the primary analysis will be used. The changes from baseline to each visit for each parameter will be calculated. Means and adjust means of each treatment group will be provided, as well as adjusted mean and associated two-sided 95% CI of the difference between treatment groups.

For the change from baseline in the amount and days of permitted pain rescue medication at each post-baseline visit, the Wilcoxon Mann Whitney test will be performed.

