2.5.6 Pooling of centers for statistical analyses

Not applicable.

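### The primary MMRM's only stated estimation method is maximum likelihood, in example code, which makes the test slightly anti-conservative (about 5.2% to 6.3% for an assumed 5 to 40 sites); REML should be named instead

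*SAP*

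**What the plan says.** SAP 2.4.4.1 describes the primary analysis as a repeated-measures ANCOVA equivalent to an MMRM. It has fixed effects for treatment, site, visit, visit-by-treatment and baseline WOMAC A1, and an unstructured covariance with a fallback order of Toeplitz, AR(1) and compound symmetry. On inference it says "The Kenward-Roger approximation will be used to estimate denominator degrees of freedom". The test is two-sided at 0.05.

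The text does not say whether the model is fitted by ML or REML. The protocol (11.4.2.1) says only repeated-measures ANCOVA, and SAP 2.5.7 on technical issues is marked not applicable. The one statement on estimation is in SAS Display 1, introduced by "An example of the SAS code is provided below (note time is modeled with the visit variable" and opening with "proc mixed data = data method = ml". Site is a class variable in that code, and SAP 2.5.6, "Pooling of centers for statistical analyses", is marked not applicable.

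Other analyses inherit this model:

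- **Continuous secondary endpoints** (7-day average WOMAC A1, WOMAC A, PTGA, COGA; SAP 2.4.4.2): "repeated-measures ANCOVA will be used as described in the description of the primary effectiveness analysis".
- **Continuous tertiary and quality-of-life endpoints** (SAP 2.4.4.4): "the same repeated-measures ANCOVA model as described in the primary analysis will be used".
- **Multiple-imputation sensitivity analyses** (SAP 2.4.4.1): "Each imputed data set will then be analyzed using the same repeated measures analysis of ANCOVA".

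**The concern.** ML estimates the covariance as if the fixed effects were known, so it divides by the number of patients rather than by what remains after the mean model is fitted. With site as an unpooled fixed effect, the number of mean parameters grows with the number of sites, and so does the downward bias. Too small a covariance gives too small a standard error, too narrow a 95% confidence interval, and a rejection rate above the stated 0.05.

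A programmer who follows the display would therefore run a confirmatory test that errs in the direction of declaring a difference. If the display is not binding, the estimation method of the primary analysis is not pre-specified. The GEE responder analysis, the Wilcoxon test for rescue medication and the Bayesian imputation step are not affected.

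**Working it through.** **Inputs from the documents.** 422 patients, 211 per group, t-test at two-sided 5% with 90% power (SAP 1.3); six post-baseline visits, at Weeks 4 to 26, and the model terms (SAP 2.4.4.1).

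**Inputs that had to be assumed.** The number of sites S is not given, so 5 to 40 is used. No dropout rate is given.

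**The plan's own figure.** The SD and the mean difference are redacted, so 211 per group cannot be reproduced. Back-solving the normal approximation gives a standardised effect of (1.960 + 1.282) × sqrt(2/211) = 0.316. Nothing below depends on it.

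**Closed form.** For the treatment contrast averaged over 26 weeks, the between-patient parameters are the intercept (1), sites (S − 1), baseline (1) and treatment (1), so p = S + 2. Then

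- SE(ML)/SE(REML): r = sqrt((422 − p)/422)
- two-sided level = 2 × P(t > r × t₀.₉₇₅), with 422 − p degrees of freedom.

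For example, with 20 sites p = 22, r = sqrt(400/422) = 0.974, and the level is 5.6%.

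| Assumed sites | p | SE ratio | Two-sided level | Level in the favourable direction (nominal 2.5%) |
|---|---|---|---|---|
| 5 | 7 | 0.992 | 5.2% | 2.6% |
| 10 | 12 | 0.986 | 5.3% | 2.7% |
| 20 | 22 | 0.974 | 5.6% | 2.8% |
| 30 | 32 | 0.961 | 6.0% | 3.0% |
| 40 | 42 | 0.949 | 6.3% | 3.1% |

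With 380 analysed patients instead of 422, the two-sided level runs from 5.2% to 6.4%.

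**First simulation.** The SAP model with unstructured covariance was fitted by both methods to 10,000 null trials per setting. Assumed: 15% monotone dropout completely at random, SD 2, correlation 0.4 + 0.6 × 0.75^lag, equal site sizes. The contrast was tested against t with 422 − p degrees of freedom in place of the full Kenward-Roger value. The Monte Carlo SE is 0.22 percentage points.

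| Assumed sites | Mean SE ratio | ML level | REML level | Trials changed to significant by ML | Changed the other way |
|---|---|---|---|---|---|
| 5 | 0.992 | 5.10% | 4.96% | 14 | 0 |
| 20 | 0.974 | 5.64% | 4.88% | 76 | 0 |
| 40 | 0.951 | 6.37% | 5.12% | 125 | 0 |

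The mean REML standard error matched the empirical SD of the estimate (20 sites: 0.177 against 0.178; 40 sites: 0.181 against 0.182). The mean ML standard error was 0.172 in both cases.

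**Second simulation, to test Kenward-Roger.** This used 6,000 null trials per setting, with no dropout or 12% dropout. The Kenward-Roger inflation of the standard error and a Satterthwaite-type df were computed on a subset and applied as averages. The inflation was only 0.01% to 0.12%, against an ML shortfall of 0.8% to 4.6%. With the inflation applied, the ML level was 5.2% to 5.5% (5 sites), 5.7% (20 sites) and 6.2% to 6.3% (40 sites). The REML level was 5.1% to 5.2%, consistent with 5% at a Monte Carlo SE of about 0.3 points.

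**The case against.** The strongest reply is that the code is only an example. The text fixes the terms, the covariance and Kenward-Roger, and nowhere commits to ML. That is true, but it leaves two readings: either the display is followed and the level is above 5%, or the method is unspecified. Both call for the same correction.

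The size also rests on a number the documents do not give. At 5 to 10 sites the level is 5.2% to 5.3%, and the simulated 5.10% at 5 sites is within one Monte Carlo SE of nominal. The 6.3% needs 40 sites of about 10.6 patients each (422/40), which nothing in the documents establishes. Marking pooling as not applicable would also fit a few large centers. This stands: the figures are conditional on the site count, and with few sites the effect is negligible.

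Two limits on scope also stand. ML and REML point estimates can differ slightly, so the finding that all changes go towards significance is a simulation result under the stated assumptions, not a theorem. In the multiple-imputation analyses ML shrinks only the within-imputation variance, so the figures above should not be read across to them.

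**Conclusion.** The concern holds. If SAS Display 1 is followed, the primary standard error and confidence interval are about 1% to 5% too narrow and the two-sided level is about 5.2% to 6.3%, for an assumed 5 to 40 unpooled sites and 422 patients. The Kenward-Roger step does not correct this, while REML restores the nominal level in simulation.

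The practical effect is modest: only a borderline primary result would be reclassified. It still deserves correction, because the error favours rejection in the confirmatory analysis, reaches four of the five secondary endpoints in the Hochberg family, and serves no purpose here. ML would be needed for likelihood-ratio comparison of mean structures, which the plan does not do; its covariance fallback depends on convergence alone.

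**What to change.** In SAS Display 1, change the estimation option from ml to reml. In the text of 2.4.4.1, add one binding sentence saying that the repeated-measures model is fitted by REML with Kenward-Roger degrees of freedom. The continuous secondary and tertiary analyses and the analysis of each imputed dataset then follow through their existing cross-references.

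The drafting cost is one word of code and one sentence. Sample size and planned power do not change, because they rest on a t-test. The procedural cost is a documented SAP revision on blinded data. Protocol section 11 provides for this but sets a deadline: "a final plan will be issued at the latest 6 to 8 weeks before final database lock". With lock planned 4 weeks after the last patient's last visit (SAP section 4), that falls 2 to 4 weeks before that visit. The SAP already carries approvals dated 30 and 31 January 2019, and protocol 11.4.2.1 has it submitted to regulatory authorities before lock, so re-approval and resubmission may be needed. The documents do not show whether that window is still open.

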2.4.4.2 Analyses of secondary efficacy endpoints

As with the primary effectiveness analysis, the secondary effectiveness analyses will be performed on the mITT population as well.

For the analysis of the change from baseline in 7-day average WOMAC A1, WOMAC A, PTGA, and COGA, repeated-measures ANCOVA will be used as described in the description of the primary effectiveness analysis.

For the analysis of WOMAC A1 responders (≥ 2 point improvement on NRS Scale) generalized estimating equations (GEE) modeling will be used. Each responder (yes/no) endpoint evaluated at multiple post-baseline visits will be analyzed using GEE for binary outcomes. A GEE model will be fitted to the responder data and will include terms for baseline measure, site, visit, treatment group and a visit-by-treatment group interaction. Hypothesis testing will be performed using least squares means based on the linear predictor of the model.

For the analysis of the percentages of positive responders, patients who discontinued the study prior to the Week 26 assessment due to either target knee-related AEs or due to lack of efficacy were classified as non-responders in the efficacy analysis. Patients who discontinued the study for other reasons had their responder status imputed using the LOCF method. The LOCF was used for all responder analyses, but not for the analysis of other parameters. No replacement on any missing or invalid data was made for the safety analyses.

No sensitivity analyses are planned for secondary efficacy endpoints in this study.

2.4.4.3 Multiplicity issues

The overall Type I Error will be set at 5%. The primary effectiveness endpoint will be tested at the 5% significance level.

The analyses of secondary effectiveness variables will be interpreted according to the Hochberg Step-Up (7) Procedure with the overall alpha set at the 0.05 level. The procedure will be implemented as follows:

The observed p-values will be sorted in descending order $p_1 > \dots > p_m$.

Term	Interpretation	Value
i	The current positioning the evaluation order	
m	The total number of comparisons	5
q	The overall level of type I error rate for the family of tests	0.05
p_i	An individual observed p-value in the i th position	
q_i	Significance level of the i th comparison	

For each evaluation i the largest p-value remaining in the set to be evaluated p_i is compared to the significance level for that comparison (q/i). If p_i is less than the significance level, it and all other p-values remaining in the set are declared statistically significant and the evaluation process stops. If this condition is not met, then the current p_i is declared, “not statistically significant” and the remaining set of observed p-values is evaluated at the next value of “ i ”. If the last p-value (p_m)

fails at the level of q/m , then all comparisons are declared to be not statistically significant. With 5 secondary endpoints, the evaluation will be conducted according to the following table:

i	q_i less than	interpretation
1	0.0500	All five tests declared significant
2	0.0250	P2, p3, p4 and p5 declared significant
3	0.0167	P3, p4 and p5 declared significant
4	0.0125	P4 and p5 declared significant
5	0.0100	P5 declared significant

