### 11.4.2.3 Multiplicity considerations

The overall Type I Error will be set at 5%. The primary effectiveness endpoint will be tested at the 5% significance level.

The analyses of secondary effectiveness variables will be interpreted according to the Hochberg Step-Up Procedure (18) with the overall alpha set at the 0.05 level. The procedure will be implemented as follows:

The observed p-values will be sorted in descending order  $p_1 > \dots > p_m$ .

Term	Interpretation	Value for synv
i	The current positioning the evaluation order	
m	The total number of comparisons	5
q	The overall level of type I error rate for the family of tests	0.05
$p_i$	An individual observed p-value in the ith position	
$q_i$	Significance level of the ith comparison	

For each evaluation  $i$  the largest p-value remaining in the set to be evaluated  $p_i$  is compared to the significance level for that comparison ( $q/i$ ). If  $p_i$  is less than the significance level, it and all other p-values remaining in the set are declared statistically significant and the evaluation process stops. If this condition is not met, then the current  $p_i$  is declared, “not statistically significant” and the remaining set of observed p-values is evaluated at the next value of  $i$ . If the last p-value ( $p_m$ ) fails at the level of  $q/m$ , then all comparisons are declared to be not statistically significant. With 5 secondary endpoints, the evaluation will be conducted according to the following table:

i	qi less than	interpretation
1	0.0500	All five tests declared significant
2	0.0250	p2, p3, p4 and p5 declared significant
3	0.0167	P3, p4 and p5 declared significant
4	0.0125	P4 and p5 declared significant
5	0.0100	P5 declared significant

Statistical comparisons of tertiary endpoints will be presented with unadjusted p-values and considered exploratory.

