2.1.3 Efficacy endpoints

The baseline value for efficacy endpoints is defined as the last available value prior to the IMP administration or last available value on or before the date of randomization if not treated, unless otherwise specified.

WOMAC scores

The WOMAC NRS 3.1 questionnaire is a self-administered, health status measure used to probe symptoms of pain (WOMAC A), stiffness (WOMAC B), and function (WOMAC C) in patients with OA of the knee (1, 3). The questionnaire consists of 24 questions relating to the patient's assessment of his/her target joint pain (5 questions), stiffness (2 questions), and physical function (17 questions). An 11-point NRS ranging from 0 (None) to 10 (Extreme) will be used to capture the patient's response to each of the questions. All responses will be recorded directly on the paper patient questionnaire (PQ), and the PQ will serve as source documentation. The patient was asked to check the box that indicated his/her amount of target joint pain, amount of stiffness, and degree of difficulty completing tasks within the past 48 hours.

The WOMAC A consists of 5 questions assessing pain symptoms while walking, using stairs, at night while in bed, sitting or lying, and standing.

The WOMAC A1 is a single question within the WOMAC A that specifically assesses target knee pain while walking on a flat surface.

The WOMAC B consists of 2 questions assessing severity of stiffness that occurs after a period of inactivity later that same day.

The WOMAC C consists of 17 questions assessing physical function while performing the following activities: stair rise, rise from sitting, standing, bending, walking, getting in/out of a car, putting on/taking off socks, rising from bed, lying in bed, getting in/out of bath, sitting, getting on/off toilet, heavy household duties, and light household duties.

The WOMAC total score is computed as the sum of the available components of the 3 subscores: WOMAC A, WOMAC B and WOMAC C. The raw total WOMAC score ranges from 0 to 240, since the sums for the components of the 3 subscores range from 0 to 50 for the WOMAC A, 0 to 20 for the WOMAC B, and 0 to 170 for the WOMAC C. The total WOMAC score will be set to missing if any of the WOMAC subscores are set to missing as defined above. The raw total WOMAC score will be standardized to the 0 to 10 scale by dividing by 24.

Patient Global Self-Assessment (PTGA)

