2.1.3.2 Secondary efficacy endpoint(s)

Secondary efficacy endpoints include the differences between treatment groups in:

- Change from baseline over 26 weeks in 7-day average walking pain score (measured by daily WOMAC A1, 7-day average WOMAC A1), WOMAC A, B, C and total, as well as PTGA, and COGA
- Percentages of positive responders over 26 weeks, where response is defined as a ≥ 2 -point improvement from baseline in the WOMAC A1 NRS

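### The plan states an overall 5% Type I error but never makes the secondary Hochberg tests conditional on the primary; under the global null the overall error is about 5.5% to 9.7%, depending on the assumed correlation.

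*SAP*

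**What the plan says.** SAP 2.4.4.3 opens: "The overall Type I Error will be set at 5%. The primary effectiveness endpoint will be tested at the 5% significance level". The secondary endpoints are then "interpreted according to the Hochberg Step-Up (7) Procedure with the overall alpha set at the 0.05 level". Protocol 11.4.2.3 opens in the same way and has the secondaries "interpreted according to the Hochberg Step-Up Procedure (18) with the overall alpha set at the 0.05 level".

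Both sections give the algorithm in full. The five secondary p-values are sorted in descending order and compared in turn with 0.05/i. At the first success, that p-value and all smaller ones are declared significant. The primary result is not an input at any step. The table of terms defines q as "The overall level of type I error rate for the family of tests".

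No linking rule appears elsewhere. The protocol synopsis, Protocol 11.4.2.1 and 11.4.2.2, SAP 2.4.4.1 and 2.4.4.2, and SAP Appendix B were checked; none makes the secondary analysis depend on the primary result.

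The plan does say which analyses are not confirmatory. Tertiary and other endpoints "will be presented with unadjusted p-values and considered exploratory" (SAP 2.4.4.4), and the subgroup analyses of the primary are also called exploratory. The secondary endpoints carry no such label.

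**The concern.** The full 5% is used twice: once on the primary and once on the secondary family. That fits a single overall 5% only if the secondary family is closed off when the primary fails. Without that rule, a trial with a non-significant primary could still report 7-day average walking pain, WOMAC A, PTGA, COGA or the responder rate as statistically significant under a stated overall control that does not hold.

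A failed primary is a realistic case. The amendment table in SAP 1.5 justifies the added endpoints, including the 7-day secondary endpoint, by noting that pain studies are in general less likely to succeed.

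**Working it through.** **Inputs.** From SAP 2.4.4.3: primary alpha 0.05, secondary family alpha 0.05, m = 5. From SAP 2.4.4.1: the primary test is two-sided. The correlations between endpoints are assumed, because the documents give none.

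**The plan's own thresholds.** 0.05/i for i = 1 to 5 gives 0.0500, 0.0250, 0.0167, 0.0125 and 0.0100. These match the table, so the Hochberg step itself is set out correctly.

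**Overall error without a gate.** This is P(primary p < 0.05, or any Hochberg rejection, when the endpoints concerned are null).

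- Upper bound: 0.05 + 0.05 = 10%.
- Two independent tests that each use exactly 5%: 1 − 0.95² = 9.75%.
- Independent endpoints, all null: Hochberg on five rejects in 4.91% of trials, so 1 − 0.95 × (1 − 0.0491) = 9.66%.

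For correlated endpoints, six normal test statistics were simulated with two-sided p-values and equal correlation ρ. The global-null columns for overall error and for a false secondary claim use 8,000,000 simulated trials. The favourable-direction and partial-null columns use 1,000,000.

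| ρ | Overall error, global null | False secondary claim with failed primary | Of these, in favour of the product | Overall error, primary and one secondary null, other four effective |
|---|---|---|---|---|
| 0 | 9.66% | 4.66% | 2.35% | 9.72% |
| 0.3 | 9.12% | 4.11% | 2.03% | 9.56% |
| 0.5 | 8.23% | 3.22% | 1.62% | 9.09% |
| 0.7 | 6.98% | 1.97% | 0.98% | 8.33% |
| 0.8 | 6.23% | 1.23% | 0.62% | 7.82% |
| 0.9 | 5.48% | 0.48% | 0.25% | 7.03% |

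The second column is 5% plus the third, up to simulation error. A repeat with 2,000,000 trials agrees with the second column to within 0.02 percentage points. In the last column the four effective secondaries have mean z = 10 and so practically always reject. The one null secondary is then tested at the full 0.05.

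**A structure closer to this trial.** Independence is the least plausible case. "The WOMAC A1 is a single question within the WOMAC A", the responder endpoint is a cut-point on the change in A1, and the 7-day score averages daily A1 ratings. So the primary and three of the five secondaries form one block. Results under the global null, 1,000,000 trials each:

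| Within A1 block | Block with PTGA and COGA | PTGA with COGA | Overall error |
|---|---|---|---|
| 0.7 | 0.5 | 0.5 | 7.59% |
| 0.8 | 0.3 | 0.5 | 7.43% |
| 0.8 | 0.5 | 0.7 | 7.06% |
| 0.9 | 0.5 | 0.7 | 6.57% |
| 0.9 | 0.7 | 0.8 | 6.09% |

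**With a gate.** If the primary is null, any false claim first requires a false rejection of the primary, so the overall error cannot exceed 5%; simulation gave 4.95% to 5.02% in both equal-correlation scenarios. If the primary is truly effective and all five secondaries are null, the error is at most that of Hochberg alone: 4.9% at ρ = 0, falling to 2.7% at ρ = 0.9.

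**The case against.** The strongest reply is that the text may mean 5% per family. It also uses the word *overall* for the secondary family alone, and the definition of q refers to a family. On that reading each family holds its level and nothing is inflated. This is a possible reading, but it does not save the text. The opening sentence sets an overall rate before any family is named, and two families at 5% do not give an overall 5%. Either the gate is missing or that sentence is wrong.

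The objections to size carry more weight. The 9.7% end needs independent endpoints, which is not credible here. At high correlation under the global null the excess is small, and only about half of the false claims favour the product: about 1% of trials or fewer once ρ reaches 0.7.

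The partial-null column is close to a worst case. With 211 per group, z = 10 is a standardised difference of 10 × √(2/211) ≈ 0.97, against about 0.32 implied by 90% power. It also requires at least two A1-based secondaries to be truly effective while A1 itself shows no effect. It should be read as a bound.

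There is also a fair point about procedure. Protocol 11 ties SAP revisions to protocol amendments and to unexpected issues in conduct or data; a missing rule is not clearly either. The SAP already carries approvals dated January 2019. This affects how the fix is made, not whether the text is wrong.

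**Conclusion.** The concern holds. No gate or alpha split is written, and the algorithm as specified can declare secondary endpoints significant after a failed primary. Under the global null the overall two-sided error is 5.5% to 9.7% for equal correlations from 0.9 to 0, and 6.1% to 7.6% under the block structures tried. These ranges rest on assumed correlations; the missing rule does not. Counting only rejections in favour of the product, the equal-correlation range is about 2.7% to 5.0% against a nominal 2.5%.

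The defect is confined to secondary claims after a failed primary. It should be fixed, but it does not threaten the primary conclusion.

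**What to change.** Before unblinding, add to SAP 2.4.4.3 a sentence to this effect: *the Hochberg procedure is applied to the secondary endpoints only if the primary endpoint is significant at the two-sided 0.05 level; otherwise the secondary p-values are nominal and descriptive.*

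In the same revision, name the five endpoints in the family. SAP 2.1.3.2 lists "WOMAC A, B, C and total, as well as PTGA, and COGA" as secondary alongside the 7-day score and the responder rate. That makes eight endpoints against m = 5, whereas Protocol 9.2.1 and SAP 2.4.4.2 have five, and SAP 2.4.4.4 treats WOMAC B, C and total as tertiary. Correct 2.1.3.2 to match.

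If the sponsor does intend 5% for each family, change the opening sentence in both documents to say so and drop the claim of an overall 5%.

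The cost is small. Protocol 11 provides for SAP revisions before database lock and says of them: "These revisions will be based on blinded review of the study and data". The change should be recorded in SAP 1.6, which now lists none. Protocol 11.4.2.3 can be aligned at the next amendment, which under Protocol 15 needs ethics committee approval; until then the SAP entry should note the difference. The primary loses no alpha. What is given up is any formal secondary claim when the primary fails. If the data have already been unblinded, secondary results after a failed primary should be reported as nominal.
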